5. STUDY POPULATION

The study population includes subjects with AA who had progressive disease during first-line treatment or who are in first or second relapse and who have not previously received any bevacizumab (BEV) or other anti-angiogenic agent, including sorafenib, sunitinib, axitinib, pazopanib, everolimus or cilengitide.

5.1. Number of Subjects and Sites

Approximately 36 subjects will be enrolled in the study 26 evaluable patients needed.

5.2. Inclusion Criteria

Any patient with a histological diagnosis of AA who meets all of the specific eligibility criteria listed below may be enrolled on this study.

1. Understand and voluntarily sign and date an informed consent document before any study related assessments/procedures are conducted.
2. Males and females > the age of 21 years at the time of the signing of the informed consent document.
3. All subjects must have histologic evidence of G3 MG and radiographic evidence of recurrence or disease progression (defined as either a greater than 25% increase in the largest bi-dimensional product of enhancement, a new enhancing lesion or a significant increase in T2 FLAIR).
4. Subjects with archival tumor tissue suitable for genetic testing must give permission to access and test the tissue; subjects without archival tumor tissue are eligible.
5. No prior treatment with BEV or any anti-angiogenesis agents.
6. At least 4 weeks from surgical resection and 12 weeks from end of radiotherapy prior to enrollment in this study, unless relapse is confirmed by tumor biopsy or new lesion outside of radiation field, or if there are two MRIs confirming progressive disease that are 8 weeks apart.
7. All AEs resulting from prior chemotherapy, surgery or radiotherapy must have resolved to NCI-CTCAE (v. 4.03) Grade ≤ 1 (except for laboratory parameters outlined below).
8. Laboratory results within 7 days prior to NOVOTTF-200A administration (transfusions and/or growth factor support may be used at the discretion of the Investigator during Screening):
 - Hemoglobin ≥ 9 g/dL.
 - Absolute neutrophil count (ANC) $\geq 1.5 \times 10^9/\text{L}$.
 - Platelet count $\geq 100 \times 10^9/\text{L}$.
 - Serum bilirubin $\leq 1.5 \times$ upper limit of normal (ULN) or $\leq 3 \times$ ULN if Gilbert's disease is documented.
 - Aspartate transaminase (AST) ≤ 2.5 ULN.
 - Serum creatinine $\leq 1.5 \times$ ULN.
9. Karnofsky Performance Status (KPS) score $\geq 70\%$.
10. Willing and able to adhere to the study visit schedule and other protocol requirements.

5.3. Exclusion Criteria

The presence of any of the following will exclude a subject from enrollment:

1. The presence of 1p19q LOH which is diagnostic for anaplastic oligodendroglioma (AO).
2. Co-medication that may interfere with study results, e.g., immunosuppressive agents other than corticosteroids. (Steroid therapy for control of cerebral edema is allowed at the discretion of the investigator. Subjects should be on a stable dose of steroids for at least 1 week prior to study beginning.)
3. Chemotherapy administered within 4 weeks (6 weeks for an IV nitrosoureas and 12 weeks for an implanted nitrosoureas wafer) prior to Day 1 of study treatment.
4. Pregnancy or breastfeeding.
5. Uncontrolled intercurrent illness including, but not limited to, ongoing or active infection requiring IV antibiotics & psychiatric illness/social situations that would limit adherence with study requirements, or disorders associated with significant immunocompromised state.
6. Known previous/current malignancy requiring treatment within ≤ 3 years except for cervical carcinoma *in situ*, squamous or basal cell skin carcinoma and superficial bladder carcinoma.
7. Any comorbid condition that confounds the ability to interpret data from the study as judged by the Investigator.

6. DESCRIPTION OF STUDY TREATMENTS

6.1. Description of Investigational Product

NOVOTTF-200A is an investigational device that will be available through a commercial use program by NovoCure.

6.2.1. Pre-Treatment Evaluation (Screening and Baseline)

Within one week prior to beginning treatment all patients will undergo the following studies:

- Baseline contrast enhanced MRI of the brain (within 2 weeks of beginning treatment).
- Complete physical examination
- Neurological status and KPS (Karnofsky performance scale).
- Complete blood count (CBC) and differential
- Biochemistry panel (Electrolytes, BUN, creatinine, bilirubin, liver enzymes, albumin, total protein, glucose, cholesterol)
- Coagulation study (PTT, INR)
- Quality of life questionnaire [the Functional Assessment of Cancer Therapy (FACT) questionnaires FACT-Brain (FACT-Br) and FACT-Cognitive Function (FACT-Cog)]

6.2.2. Treatment Administration and Schedule

All patients will begin treatment within 1 week from screening/baseline evaluation. Treatment will be initiated in an outpatient clinic by the investigator. In addition to clinical evaluation, the investigator will perform the following actions for the treatment arm patients:

- Train the patient in using the device:
 - Battery replacement and recharging
 - Turning the device on and off
 - Disconnecting and reconnecting the electrodes from the device for personal needs
 - How to handle device error messages
 - What adverse events can be expected during the treatment.
 - How to handle irritated skin
 - What to do in case of new or worsening clinical signs (call investigator)
- Review the baseline MRI and decide where to place the electrodes
- Place the electrodes
- Connect the electrodes to the device (through the connection cable)
- Turn on the device

The device will be set in advance with the following treatment parameters:

- Frequency – 200 kHz
- Output current – 707 mA RMS
- Number of field directions – 2
- Duty cycle – 1 sec in each direction

The patients will continue treatment at home after being trained in device use.

The patients will receive multiple 1 month courses of continuous NovoTTF-200A treatment. The decision to add each additional treatment course will depend on the lack of treatment related

serious adverse events which reappear upon re-challenge and lack of clinical disease progression. After initiation of treatment by the physician in the outpatient clinic, maintenance of NovoTTF-200A treatment will be performed by NOVOTTF-200A technicians. All technical aspects of the treatment are handled by these technicians at the patients' homes.

The following actions are performed by the technician:

- Periodic download of device log
- Replacement of faulty equipment
- Device, electrode and accessory accountability tracking, and requests for replacements from NovoCure
- Problem solving – by phone between visits to the technical clinic or directly during these visits
- For technical support the patient will contact the local technical clinic. A list of clinics and their contact information will be supplied to the patients separately. If the patient is unable to get a hold of the local device technician or if the patient has technical problems with the device beyond working hours he/she should call the following Toll free number for NovoCure's international support center: [name] (for USA).

Once every month from baseline, until treatment termination, all patients will be seen in the outpatient clinic where they will be assessed clinically and undergo routine laboratory examinations. The follow-up window for these visits is +/- 7 days if the visit occurs prior to the 6 month follow-up window and +/- 14 days on or after the 6 month visit window. Follow up window from the 12 month visit onward will be +/- 1 month.

Medical follow-up and routine laboratory exams for all patients will continue once per month for 2 months following end of treatment. After this post-progression follow up period, patients will be followed by monthly telephone interview until death.

The specific locations of each electrode set will be determined by the treating investigator using the NovoTal software.

6.2.3. Ongoing Evaluation and Periodic Evaluation

During electrode replacement, the skin below the electrode will be inspected by the physician (during follow up visits) and by the patient himself or herself (at home). In the event of significant skin breakdown (leading to pain or bleeding) or evidence of infection, the electrode will be moved to an alternate site. Skin breakdown and/or infection will be treated according to the treating physician's clinical judgment based on a dermatologist's recommendation. Skin breakdown or evidence of infection, either of which requires a break in NovoTTF-200A treatment greater than 3 days, will be captured as an Adverse Event. Mild to moderate contact dermatitis is expected to appear beneath the electrode gel during the first or second treatment course. This condition will be treated as follows:

1. Electrode location will be shifted between two alternate sites at every electrode change.
2. If skin is inflamed – apply 0.1% hydrocortisone ointment.
3. If skin is breached (abrasions, micro-ulcerations, oozing, open sores) or infected –

- a. Discontinue hydrocortisone and prescribe a Mupiricin (e.g. Bactroban) ointment.
4. In the case of skin blistering – apply Silver Sulfadiazine (e.g. Silverdine ointment). In the case of known hypersensitivity to sulfa containing compounds the treatment outlined will not be offered and a dermatologist will be consulted.
5. In any case where the patient does not notice an improvement in skin sores, infection or blistering within 2 weeks of starting one of the treatments outlined above, the patient will inform the investigator and a dermatological consult will be obtained.
6. Oral antihistamines and analgesics will be prescribed at the investigators' discretion to control pruritus and pain.

Patients will undergo the following studies or review every month until treatment termination:

- Physical examination
- Neurological status
- Quality of life questionnaire (the Functional Assessment of Cancer Therapy (FACT) questionnaires FACT-Brain (FACT-Br) and FACT-Cognitive Function (FACT-Cog)) – every two months until treatment
- termination
- Blood exams (CBC, Chemistry, Coagulation – for patients receiving anti-coagulants)
- Steroid dose *if applicable*
- Record of Adverse Events

The patients will have a contrast MRI of the head performed after every two months. In case of clinical progression an MRI will be performed within a week.

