A pilot study was performed on ten recurrent GBM patients treated with the NovoTTF- 200A device. All patients underwent surgery and radiotherapy for the primary tumor. Only 1 patient was chemotherapy naïve, the rest having received either temozolomide or other chemotherapeutic agents, as adjuvant treatment, prior to recurrence.

All patients were treated with multiple four-week treatment courses using continuous, 24-hour a day, 200 kHz, 0.7 V/cm TTFields. TTFields were applied through two sets of opposing insulated electrode arrays and alternated at a 1 second duty cycle between two perpendicular field directions through the tumor. Patients completed between 1 and 15 treatment courses leading to maximal treatment duration of 14.5 months. Overall, more than 70, 4 week treatment courses were completed (> 7 courses per patient on average).

The treatment was well tolerated with no treatment related serious adverse events seen in any of the patients. Patients received treatment on average about three quarters of the scheduled time. Considering the continuous nature of NovoTTF treatment (i.e., 24 hours a day for many months) this figure indicates that compliance with treatment was very high, with patients taking very few days off treatment and stopping only for short periods of time during treatment for personal needs.

Mild to moderate contact dermatitis appeared beneath the electrode gel in 8 of the 10 patients during treatment. In most cases this dermatitis appeared for the first time during the second treatment course. The skin reaction improved with use of topical corticosteroids. Regular relocation of the electrode arrays was necessary in order to allow for continuous treatment.

The median progression free survival (PFS) of the patients in this study exceeded historical controls (26.1 weeks versus 9 weeks, respectively). The PFS at 6 months (PFS6) was 50% compared to 15% in historical controls. Median overall survival was 62 weeks.

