9.2. Safety Analysis

All subjects will be evaluated for safety analysis if they receive NOVOTTF-200A. The safety data will be presented in individual listings and summary tables, including frequency tables for adverse events and listings of abnormalities for laboratory variables.

Safety analysis:

- *Safety and tolerability of NOVOTTF-200A treatment will be based on the incidence and severity of adverse events and toxicities. Toxicities will be assessed according to the “Common toxicity criteria (CTC), version 4.03”.*

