the adverse event, serious adverse event, violation, deviation, or unanticipated problem. Serious violations, deviations/violations, and unanticipated problems that require prompt reporting to the DSMB must be entered into OnCore within 24 hours of knowing of the event. Definitions of events are provided below.

Definitions

Adverse event (AE) - An adverse event is any untoward medical experience or change of an existing condition that occurs during or after treatment, whether or not it is considered to be related to the protocol intervention.

Unexpected Adverse Event [21 CFR 312.32 (a)] – An adverse event is unexpected if it is not listed in the investigator’s brochure and/or package insert; is not listed at the specificity or severity that has been observed; is not consistent with the risk information described in the protocol and/or consent; is not an expected natural progression of any underlying disease, disorder, condition, or predisposed risk factor of the research participant experiencing the adverse event.

Expected Adverse Event - Any event that does not meet the criteria for an unexpected event OR is an expected natural progression of any underlying disease, disorder, condition, or predisposed risk factor of the research participant experiencing the adverse event.

Serious Adverse Event (SAE) [21 CFR 312.32] - defined as *any expected or unexpected adverse event* that result in any of the following outcomes:

- Death
- Is life-threatening experiences (places the subject at immediate risk of death from the event as it occurred)
- Unplanned hospitalization equal or greater than 24 hours)) or prolongation of existing hospitalization
- A persistent or significant disability/incapacity
- A congenital anomaly/birth defect
- Any other adverse event that, based upon appropriate medical judgment, may jeopardize the subject’s health and may require medical or surgical intervention to prevent one of the outcomes listed above (examples of such events include allergic bronchospasm requiring intensive treatment in the emergency room or at home, blood dyscrasias of convulsions that do not result in inpatient hospitalization, or the development of drug dependency or drug abuse).

Unanticipated problem (UP) - Any incident, experience or outcome that **meets all three** of the following criteria:

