An incident that significantly affects subject safety or data integrity (e.g. wrong dosage of drug administered, safety procedures not being conducted at specific time points).	5 days from the date the PI is aware of the event
All incidents that occurred during the study	At the time of progress review as aggregate reports

UNANTICIPATED PROBLEMS

Unanticipated problems that are adverse events must be reported within 24 hours of reporting to the IRB for review.

Treatment with the NOVOTTF-200A is not expected to cause any serious side effects. However, it is possible that investigational treatment will cause any of the following:

- Local warmth and tingling sensation beneath the electrodes
- Allergic reaction to the plaster or to the gel
- Skin breakdown
- Infection at the sites of electrode contact with the skin
- Electrode overheating leading to pain and/or local skin burns
- Headache
- Fatigue
- Seizures

Adverse events and complications associated with the underlying AA disease process, which are unlikely but unknown if related to treatment with NOVOTTF-200A might include the following adverse events:

- Seizure, including Status Epilepticus
- Neurological and functional decline
- Headaches, nausea and/or vomiting
- Death

As defined by the ICH Guidelines for Good Clinical Practice E2A (CPMP/ICH/377/95), an adverse event (AE) is any untoward medical occurrence in a patient administered a medicinal product and which does not necessarily have to have a causal relationship with this treatment. An adverse event can therefore be any unfavorable and unintended sign (for example, an abnormal laboratory finding), symptom, or disease temporally associated with the use of a medicinal product, whether or not considered related to this medicinal product. Adverse events include the following:

- All suspected medication adverse reactions
- All reactions from medication overdose, abuse, withdrawal, sensitivity, or toxicity.
- Apparently unrelated illnesses, including the worsening of a preexisting illness
- Injury or accidents. Note that if a medical condition is known to have caused the injury or accident (a fall secondary to dizziness), the medical condition (dizziness) and the accident (fall) should be reported as 2 separate adverse events.
- Abnormalities in physiological testing or physical examination findings that require clinical intervention or further investigation (beyond ordering a repeat [confirmatory] test).

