- Laboratory abnormalities that require clinical intervention or further investigation (beyond ordering a repeat [confirmatory] test) unless they are associated with an already reported clinical event. Laboratory abnormalities associated with a clinical event (elevated liver enzymes in a patient with jaundice) should be captured in the source documents.

Each adverse event is to be classified by the investigator as serious or non-serious. This classification of the gravity of the event determines the reporting procedures to be followed.

Grading of an Adverse Event:

The descriptions and grading scales found in the revised NCI Common Toxicity Criteria (CTC) version 4.03 will be utilized for assessing severity of adverse events. If the toxicity is not characterized adequately by the NCI toxicity scale, the investigator will use the adjectives MILD, MODERATE, SEVERE to describe the maximum intensity of the adverse event. For purposes of consistency, these intensity grades are defined as follows:

- MILD Grade 1 Transient or minimal symptoms, no change in activity or need for medication
- MODERATE Grade 2 Symptomatic change, interferes to some extent with patient's usual function
- SEVERE Grade 3 Incapacitating, significantly interferes with patient's usual function

Determination of Causality of Adverse Events

The relationship of the adverse event to the study treatment must be specified using the following definitions:

None:

The event is clearly related to an event that may be due to environmental or accidental occurrence or other factors such as the subject's clinical state, therapeutic interventions, or concomitant drugs administered to the subject.

Unlikely

The event is most likely produced by other factors such as the subject's clinical condition, therapeutic interventions, or concomitant drugs administered to the subject **and** does not follow a known response pattern to the study device.

Possible

The event follows a reasonable temporal sequence from the time of drug administration or use of device, **and/or** follows a known response pattern to the study drug or device, **but** could have been produced by other factors such as the subject's clinical condition, therapeutic interventions, or concomitant drugs administered to the subject.

Probable

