Any potential unanticipated adverse device effect (UADE) will be reported to the local IRB within 10 days of the investigator learning of the event. The investigator will investigate whether the adverse event is a UADE and, if so, report the UADE to the manufacturer, as soon as possible but no later than 3 days after first learning of the event. Expedited report for FDA submission to follow within 10 working days after the investigator first learning of the event.

The report will contain the following:

- The initials of the subject, subject ID #, protocol # and title

- The date the event occurred
- A description of the UADE
- An explanation of how the UADE was handled
- A description of the subject's condition
- Indication if the subject remains on the study
- Indication if the event is considered related to the NovoTTF-200A
- Indication if an amendment to the protocol and/or consent form is recommended as a result

Eliciting Adverse Event Information

The investigator is to report all directly observed adverse events and all adverse events spontaneously reported by the trial patient using concise medical terminology. In addition, each subject will be questioned about adverse events at each clinic visit following initiation of treatment. The question asked will be, “Since your last clinic visit have you had any health problems?”

Adverse Event Reporting Period

The adverse event reporting period will begin immediately following initiation of treatment with the NOVOTTF-200A device. Adverse events will be collected for two months following treatment termination. All adverse events that occur in trial patients during the adverse event reporting period specified in the protocol must be reported on the CRFs, whether or not the event is considered study treatment-related. In addition, any known untoward event that occurs beyond the adverse event reporting period that the investigator assesses as possibly related to the investigational medication/product should also be reported as an adverse event.

Follow-up of Unresolved Adverse Events

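### Section 6.2.3 captures skin breakdown or infection as an adverse event when the device is stopped for more than 3 days; section 10 has no such threshold, and nothing says which rule governs

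*Combined protocol and SAP*

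**What the plan says.** Section 6.2.3 describes how skin under the electrodes is inspected and managed. For breakdown or evidence of infection it adds a recording instruction: "either of which requires a break in NovoTTF-200A treatment greater than 3 days, will be captured as an Adverse Event". The next sentence turns to contact dermatitis, which is expected in the first or second course, and sets no recording rule for it. Section 6.2.3 also lists a monthly record of adverse events, without a threshold.

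Section 10.1 is broader. It defines an adverse event as "any untoward medical experience or change of an existing condition that occurs during or after treatment". Among the things that count it includes "Abnormalities in physiological testing or physical examination findings that require clinical intervention or further investigation". Where CTCAE does not characterise an event adequately, the fallback scale begins at a mild Grade 1, described as "Transient or minimal symptoms, no change in activity or need for medication". On recording it says: "All adverse events that occur in trial patients during the adverse event reporting period specified in the protocol must be reported on the CRFs". It also names skin breakdown and infection at the electrode sites among the possible effects of treatment, and it sends expected events of Grades 1 to 5 to the DSMB in aggregate.

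Section 9.2 states what the data are for: "Safety and tolerability of NOVOTTF-200A treatment will be based on the incidence and severity of adverse events and toxicities".

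**The concern.** The 3-day condition does nothing unless breakdown or infection with a shorter break, or none, is meant to go uncaptured. It is also the only recording instruction specific to skin events, and it stands beside the management steps that staff will consult when such an event occurs. A coordinator could reasonably apply it and leave out events that section 10.1 requires.

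These events are not trivial. Section 6.2.3 is concerned with breakdown that leads to pain or bleeding, and with breached or infected skin that is given a prescribed ointment. Its first response to significant breakdown or infection is to move the electrode, which may allow treatment to go on without a long break.

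At stake is a secondary objective, safety, reported through the adverse event tables of section 9.2. Section 8.1 also plans to look for factors that predict adverse reactions. If 6.2.3 decided what was recorded, then for breakdown and infection that analysis would in effect look for predictors of a long device interruption.

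**Working it through.** The plan states no figure on this point, so there is none to reproduce. The check is to apply the two rules to the same events and then ask whether the effect can be sized.

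**Step 1. Apply each rule to the same event.**

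| Skin event | Section 6.2.3 read literally | Section 10.1 |
|---|---|---|
| Breakdown or infection, break of more than 3 days | Captured | Captured |
| Breakdown or infection, break of 3 days or less | Not captured | Captured |
| Breakdown or infection, electrode moved, no break | Not captured | Captured |
| Contact dermatitis | No recording rule given | Captured |

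The second and third rows are the contradiction. Under section 10.1 those events qualify on the general definition. When found on examination and treated, they also qualify as findings that need clinical intervention. The fourth row is a gap in 6.2.3 and not a contradiction.

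**Step 2. Look for a rule of precedence.** Section 6.2.3 does not say that it overrides section 10, and section 10.1 makes no exception for skin. Section 8 says that all adverse events will be documented, which agrees with section 10.1 but does not mention 6.2.3.

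**Step 3. Try to size the effect.** Let p be the proportion of treated patients with breakdown or infection. Let f be the share of those patients with at least one break of more than 3 days.

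- Incidence if section 10 is followed: p.
- Incidence if 6.2.3 is followed literally: p × f.
- Relative shortfall: (p − p × f) / p = 1 − f.

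Neither p nor f is in the documents. The shortfall depends on f alone, and f can lie anywhere from 0 to 1. Assumed values show the range: f = 0.10 gives a shortfall of 90%, f = 0.25 gives 75%, f = 0.50 gives 50%, and f = 1 gives none. If section 10 is followed, the shortfall is nil whatever f is.

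**Step 4. Test whether the quoted skin rates can stand in for p.** Section 1.2 gives two. In the pilot, "Mild to moderate contact dermatitis appeared beneath the electrode gel in 8 of the 10 patients during treatment", which is 80%. In the phase III trial, mild rash in 14% and moderate rash in 2% make 16%. With 36 patients (section 5.1), full recording would give 36 × 0.80 = 28.8 or 36 × 0.16 = 5.8 patients. These are rates of dermatitis and rash, which the threshold sentence does not cover, and they differ fivefold (80 / 16 = 5). Neither can serve as p for breakdown or infection.

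**The case against.** The strongest reply is that 6.2.3 never says only. It says that events with a long break will be captured, and it can be read as singling those out without releasing staff from the general duty. That duty is firm: events "must be reported on the CRFs, whether or not the event is considered study treatment-related". Patients are also asked about health problems at each clinic visit, and serious skin events are caught by the SAE rules in sections 10.2.2 and 10.5.1 whether or not the device is stopped. The primary endpoint is untouched, and stopping for intolerability rests on clinical judgement and not on a count of skin events.

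Most of this stands. It limits the point to non-serious breakdown and infection, and it makes the loss a risk and not a certainty. It does not remove the contradiction, because the reply gives the 3-day condition no work to do and the documents do not choose between the readings.

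A reader might infer more than the text supports, in three ways.

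- **That the device's main toxicity will be undercounted.** The threshold covers breakdown and infection. The effect cited most often in the synopsis is skin irritation and heat sensation.
- **That the reported rate would fall from 80% to some 4–20%.** This takes the pilot's dermatitis rate, assumes that 5–25% of the 28.8 patients have a long break, and arrives at 1.4 to 7.2 of 36. The arithmetic is right, but it applies a rule for breakdown to a rate of dermatitis, with a share that the documents do not give.
- **That the rates could not be compared with the earlier device trials.** Section 1.2 does not give those trials' capture rules, so this cannot be judged. Nor do the documents give data showing that most skin events avoid a long break. The pilot's account of few days off treatment is qualitative.

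**Conclusion.** The point holds as a contradiction between two recording rules. Under 6.2.3 read literally, non-serious breakdown or infection with a break of 3 days or less, or with none, is not captured; under section 10 it is. The incidence and severity of these effects may therefore be underestimated, or may depend on which section a staff member happened to follow. The shortfall is 1 − f if 6.2.3 is applied and nil if section 10 is applied. With f and the underlying rate both absent from the documents, no figure can be put on it.

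The conclusion rests on one reading: that a stated threshold implies no capture below it. It should be fixed before data are collected, since skin is partly inspected by patients at home and unrecorded events may be hard to recover later. It does not affect the PFS6 estimate.

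**What to change.** Delete the 3-day condition from section 6.2.3. Put in its place a sentence saying that all skin events, including contact dermatitis, are recorded as adverse events under the section 10 rule, with CTCAE 4.03 grade, start and stop dates and relation to the device. Record any treatment interruption under action taken (section 10.2.6), so that the information on long breaks is kept without deciding whether the event is counted. This concerns data capture only and leaves the skin management steps as they are.

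The cost is an edit of a sentence or two, slightly more CRF entry, and possibly a higher reported rate of skin events.
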